YEDITEPE UNIVERSITY

STUDY PROTOCOL AND STATISTICAL ANALYSIS PLAN

The Acute Influence of Proprioceptive Neuromuscular
Facilitation on Cervical Proprioception and Range of Motion.

Date: 25/02/2019

NCT Number:
NCT04045106

Prepared by:

[name]

ISTANBUL/TURKEY

Study Summery

Title	The acute influence of Proprioceptive neuromuscular facilitation on cervical proprioception and range of motion.
Methodology	Randomized, controlled trial, double blinded study
Study Duration	The estimated time for participants recruitment, screening and protocol implantation is 20 days
Study Location	University Labs
Subjects	120 healthy subjects randomized to 3 arms: 2 treatment and 1 control Inclusion criteria: To determine if a participant is healthy a score of 5 or less on the neck disability index will be used, no history of cervical trauma, rheumatic diseases, whiplash syndrome, no history of surgeries to the neck, face and shoulders, no history of cancer, no history of systemic diseases, age of 18 or above and able to understand and follow instructions.
Assessment	Cervical Proprioception using cervical range of motion (CROM) instrument, Active Range of motion (AROM) using CROM instrument, Muscle strength using a myometer device.
Intervention	PNF Pattern: Dynamic of reversals technique, PNF stretching: contract-relax-antagonist contract (CRAC) technique, control group: ineffective passive ROM.
Statistical Methodology	Statistical analyses will be performed using SPSS software version 25. Descriptive analyses will be presented using means and standard deviations for continuous data and frequencies and percentages for categorical data. The variables investigated using Kolmogorov Smirnov test to determine whether or not they are normally distributed. Since the variables are normally distributed, ANOVA will be used to compare the means of the groups., Levene test will be used to assess homogeneity of variances. When an overall significance will be observed, pairwise post-hoc tests will be performed using Tukey's test. Since the variables are not normally distributed Kruskal-Wallis test will be used to compare the groups. The Mann-Whitney U test will be performed to test the significance of pairwise differences using Bonferroni correction to adjust for multiple comparisons. Since the variables are normally distributed, the effect of time change in measurements will be investigated by Repeated Measures ANOVA test. Greenhouse-Geisser correction will be used when sphericity assumption is violated. Since the variables are not normally distributed Friedman test will be used. The Wilcoxon test will be performed to test the significance of pairwise differences using Bonferroni correction to adjust for multiple comparisons. A 5% type-I error level was used to infer a statistical significance.

Background information:

Proprioception is the ability to sense the information raised from the musculoskeletal system regarding the movement and position of body part in space, there are many types of proprioceptors in the body such as skin, joint capsule and connective tissue but the largest contributors to joint position sense are the intermuscular receptors which are golgi tendon organs and muscle spindles.

The cervical region has high density of muscle spindles that allow a great precision of movement while also providing adequate proprioceptive information to control head position and movement and for eye-head coordination.

Proprioceptive neuromuscular facilitation (PNF) are synergistic pattern of movement with the emphasis of facilitating normal movement, the proposed mechanism for some types of PNF that they are reliant on the facilitation of golgi tendon organs and muscle spindles which are responsible for two reflexes 1. autogenic inhibition 2. Reciprocal inhibition, although there is conflicting evidence regarding the mechanisms of PNF the beneficial effects are well established on many conditions like range of motion, neuromuscular functions, lymphedema and many more.

Most of the studies that tested PNF on the cervical region measured range of motion, flexibility and strength. Studies conducted to influence cervical proprioception used multiple interventions such as head relocation practice, eye/head coordination exercises, muscle vibration, mental training, strength and motor control exercises.

Due to the importance of cervical proprioception and the lack of studies in literature, the Purpose of this study is to investigate the acute influence of proprioceptive neuromuscular facilitation on cervical proprioception, range of motion and strength.

Study Design: This is a double-blinded randomized controlled trial. Participants were not aware of their assigned group, also the assessor was blinded to group allocation.

Sample Size: The sample size was calculated by using G*Power 3.1.7 for Windows (G*Power©, University of Dusseldorf, Germany), by using f family test ANOVA repeated measures and between factors, with statistical power of 0.80 (1-B error Probability) and alpha error level probability of 0.05 and effect size of 0.25 with number of measurements being 2, which total to 120 participants.

Participants will be recruited from university campus by directly asking students from classes if they can volunteer by explaining that the trial will involve the cervical region, also mentioned that is one-time session that can take up to an hour. Participants then will be handed consent forms that included more details about the trial.

Inclusion Criteria:

- Neck disability index score of 5 or less
- Able to understand and follow instructions
- Above 18 years old

Exclusion Criteria:

- Cervical trauma
- History of cervical inter-vertebral disc pathology
- Rheumatic diseases
- Whiplash syndrome
- History of surgeries to the neck, face and shoulders
- History of systemic diseases

Randomization and Procedures Randomization done by a person external to the study. Participants that signed the consent form and meet the inclusion criteria were assigned a number which corresponded to one of the three groups. Participants were asked to enter a room where the assessor performed the first measurements, then participants were asked to go to a separate room where the treatment methods took place. The therapist corresponded the number of the participant to the randomization sheet and applied the assigned treatment. After that participants were asked to go back to the first room for the second measurement. Participants were asked not to make a comment to the assessor but they can direct any question to the therapist.

ASSESSMENT METHODS

Cervical Proprioception: The cervical proprioception will be done using cervical range of motion instrument (CROM, Performance Attainment Associates, Lindstrom, MN, USA) using the joint position accuracy method of proprioception assessment, the device is made of a plastic frame that rest over the head, nose and ears, with a strap to secure it, it has three inclinometers attached to the frame, one in the sagittal plane, the second in the frontal plane and the third in the horizontal plane, which makes able to measure all 6 directions of movement. This instrument was reliable and valid to assess cervical proprioception, the chosen target angle is 30 degrees.

Cervical proprioception was done for flexion, extension, right side bending, left side bending, right and left rotation.

Participants will be asked to sit and put on the CROM instrument, then they will be instructed to start moving their head to one of directions then the assessor will stop them at 30 degrees and tell them to feel the amount of movement and muscle tension, this will be repeated 3 times as a reference, then they will be asked to do the movement with the eyes closed until they reach the target angle, this will be repeated for 3 times, this will be done for each direction and the assessor will record the results.

Range of Motion and Muscle Strength Measurement:

Active Range of motion (AROM) will be measured using CROM instrument, the validity and reliability of CROM to assess ROM is well documented in the literature, AROM was taken for all movement directions.

Muscle strength will be measured using a myometer device (microFET2™ Hoggan Health Industries, Inc, West Jordan, Utah), cervical flexors, extensors, right and left rotators and right and left lateral flexors muscle strength will be measured.

Intervention Methods

As discussed earlier, participants were allocated to three groups, these are PNF pattern, PNF stretching and a control group.

PNF patterns will be performed using Dynamic of reversals technique which is characterized as active motion alternating from one direction (agonist) to the opposite (antagonist) without relaxing.

The cervical patterns consisted of 1- Cervical flexion with right rotation followed by extension with left rotation. 2- Cervical flexion with left rotation followed by extension with right rotation.

The participants will be asked to sit on a chair, the therapist will perform the pattern of movement himself then passively apply the pattern on the participant then ask the participant to perform the pattern, and the therapist will observe and correct the movement if it was done improperly. then participants will be told that the therapist will resist their movement, they will be instructed to keep breathing normally and to report any discomfort and/or pain. After mastering the pattern, the therapist will place one hand on the participant's mandibular and the other hand approximately between parietal and occipital bones to apply resistance throughout the ROM, each pattern will be performed for 3 sets of 10 repetitions with 1-2-minute rest between sets.

PNF stretching will be done using contract-relax-antagonist contract (CRAC) technique for cervical flexors, extensors, right and left lateral flexors, right rotators and left rotators. This will be done for 6 repetitions with hold for 6 seconds in a position of stretch and submaximal isometric contraction for 6 seconds, 1-2-minute rest will be given before changing the target muscle group.

Control Participants allocated to the control group will receive ineffective passive ROM for 10 repetitions for flexion, extension, right and left side bending and right and left rotation, it will be done from neutral position to the limit of motion without causing any stretch to the muscle.

Statistical Analysis Plan:

Statistical analyses will be performed using SPSS software version 25. Descriptive analyses will be presented using means and standard deviations for continuous data and frequencies and percentages for categorical data. The variables investigated using Kolmogorov Smirnov test to determine whether or not they are normally distributed. Since the variables are normally distributed, ANOVA will be used to compare the means of the groups., Levene test will be used to assess homogeneity of variances. When an overall significance will be observed, pairwise post-hoc tests will be performed using Tukey's test. Since the variables are not normally distributed Kruskal-Wallis test will be used to compare the groups. The Mann-Whitney U test will be performed to test the significance of pairwise differences using Bonferroni correction to adjust for multiple comparisons. Since the variables are normally distributed, the effect of time change in measurements will be investigated by Repeated Measures ANOVA test. Greenhouse-Geisser correction will be used when sphericity assumption is violated. Since the variables are not normally distributed Friedman test will be used. The Wilcoxon test will be performed to test the significance of pairwise differences using Bonferroni correction to adjust for multiple comparisons. A 5% type-I error level was used to infer a statistical significance.

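### The stated power of 0.80 at N=120 belongs to a test on the pre/post average, not to the treatment comparison that the analysis plan describes

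*Combined protocol and SAP*

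**What the plan says.** The Study Summary describes "120 healthy subjects randomized to 3 arms: 2 treatment and 1 control". The Sample Size section says the number was obtained "by using f family test ANOVA repeated measures and between factors, with statistical power of 0.80 (1-B error Probability", at alpha 0.05, with "effect size of 0.25 with number of measurements being 2, which total to 120 participants". It gives no correlation between the two measurements, and does not say which outcome, time point or contrast the 0.25 describes.

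Randomization and Procedures fixes the order of events: the "assessor performed the first measurements, then participants were asked to go to a separate room where the treatment methods took place", and "After that participants were asked to go back to the first room for the second measurement". One measurement is therefore before treatment and one after.

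The Statistical Analysis Plan, repeated in the Statistical Methodology row of the Study Summary, has three relevant statements. For normal data, "ANOVA will be used to compare the means of the groups", with Tukey's test for pairs and Levene's test for equal variances. For non-normal data, "Since the variables are not normally distributed Kruskal-Wallis test will be used to compare the groups", with Bonferroni-corrected Mann-Whitney tests. Separately, "the effect of time change in measurements will be investigated by Repeated Measures ANOVA test", with Friedman's test as the rank alternative. Neither group-comparison sentence says whether pre, post or change values are compared. The repeated-measures sentence mentions neither a group factor nor a group-by-time term.

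**The concern.** In a repeated-measures design, the between-factors test compares arms on the mean of all measurements. Here that mean includes a value taken before anyone is treated, when randomized arms can differ only by chance. If treatment shifts only the second measurement, the difference between arms in the average is half the difference after treatment. The test that was sized is thus an indirect way to look for a treatment effect, and the analysis plan does not say that it will be used.

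This is the only power statement in the document. A reader will take 0.80 as the chance of detecting a difference between arms, but it is not tied to either group test that the plan names. With the time point left open, the choice between post values and change can also be made after the data are seen.

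**Working it through.** **Inputs from the documents:** k=3 arms, m=2 measurements, f=0.25 (read as Cohen's f), alpha 0.05, target power 0.80, N=120.

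**Assumptions, none stated in the documents:** equal allocation, equal pre and post variances, an effect only after treatment, one measure, and pre-post correlation rho of 0.3, 0.5 or 0.7. Power is from the noncentral F distribution with noncentrality lambda.

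**1. Reproducing 120.** For the between-factors test, lambda = f²·N·m/(1+(m−1)·rho), df 2 and N−3. At rho=0.5, lambda = 0.0625×120×2/1.5 = 10, df 2 and 117, power 0.805. N=117 gives 0.794, so 120 is the smallest balanced size. It is the answer only for rho between about 0.479 and 0.517. At rho = 0, 0.3, 0.7 and 0.9 the same formula gives 81, 105, 135 and 150.

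**2. Other candidate tests do not give 120.**

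| Test | Noncentrality | N for power 0.80 |
|---|---|---|
| Group-by-time interaction | f²·N·m/(1−rho) | at most 81 (rho=0); 42 at rho=0.5 |
| Within (time) effect | f²·N·m/(1−rho) | at most 66 (rho=0); 36 at rho=0.5 |
| Group-by-time interaction | f²·(N−k) | 162 |
| Within (time) effect | f²·(N−k) | 132 |
| One-way ANOVA, one time point | f²·N | 159 |

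The maxima of 81 and 66 are over non-negative rho. The text and the number both point to the between-factors test.

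**3. Power at N=120 for the possible treatment comparisons.** Let F be the effect size on the post-treatment value.

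- Pre/post average (the sized test): lambda = (F/2)²·N/((1+rho)/2), df 2, 117
- ANOVA on post values: lambda = F²·N, df 2, 117
- ANOVA on change: lambda = F²·N/(2(1−rho)), df 2, 117
- ANCOVA of post on pre: lambda = F²·N/(1−rho²), df 2, 116

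*Reading A: 0.25 is on the post-treatment value (F=0.25).* For post values lambda = 0.0625×120 = 7.5. At rho=0.5, lambda is 2.5 for the average, 7.5/1 = 7.5 for change, and 7.5/0.75 = 10 for ANCOVA.

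| rho | Average (sized test) | ANOVA post | ANOVA change | ANCOVA |
|---|---|---|---|---|
| 0.3 | 0.30 | 0.68 | 0.52 | 0.72 |
| 0.5 | 0.27 | 0.68 | 0.68 | 0.80 |
| 0.7 | 0.24 | 0.68 | 0.89 | 0.93 |

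*Reading B: 0.25 is on the pre/post average.* With an effect only after treatment, F = 2×0.25 = 0.50.

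| rho | Average (sized test) | ANOVA post | ANOVA change | ANCOVA |
|---|---|---|---|---|
| 0.3 | 0.86 | 0.999 | 0.988 | above 0.999 |
| 0.5 | 0.80 | 0.999 | 0.999 | above 0.999 |
| 0.7 | 0.75 | 0.999 | above 0.999 | above 0.999 |

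**4. Rank tests.** Simulation under Reading A (10,000 replicates, 40 per arm, normal data, rho 0.3 / 0.5 / 0.7) gives Kruskal-Wallis on post values 0.66 / 0.66 / 0.65 and on change 0.50 / 0.66 / 0.87.

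**The case against.** **The trial is not shown to be underpowered.** This stands. A reader might infer a shortfall, or that 120 was miscalculated. The documents support neither: 120 reproduces, and under Reading B every group comparison listed in the analysis plan for normal data has power of at least 0.988.

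**Power is not undefined.** This also stands. It can be computed once the time point, the target of the 0.25 and the correlation are given. What can be said is that these three are unstated.

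**A repeated-measures model with a group factor would produce the sized test.** True, and the plan is silent on a group factor rather than excluding one. But it assigns that model to change over time, and even with a group factor the between-group test would be on the average that includes the pre-treatment value. It also follows that the 0.24 to 0.30 for the average under Reading A should not be quoted as the trial's power, because the plan does not name that test.

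**ANCOVA goes further than the gap requires.** Naming the time point, the effect size target and the correlation would close the gap in the text. ANCOVA is nevertheless worth adopting: it uses a baseline already collected and exceeds ANOVA on post or change values at each correlation shown under Reading A.

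**Conclusion.** The concern holds as a mismatch between the sized test and the described analysis. The 0.80 is for the between-group effect on the pre/post average at a correlation of about 0.5. The plan's group comparison has no stated time point, and its repeated-measures analysis is for time only. The 0.80 therefore does not carry over to the treatment comparison.

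The size depends on what the plan leaves out. For the named group ANOVA at N=120, power runs from 0.52 to 0.89 if 0.25 is on the post-treatment value, and is 0.988 or higher if it is on the average. Both ranges rest on the assumptions listed in the working. They apply to a single measure, whereas the protocol lists six directions each for proprioception, range of motion and strength and designates no primary one. This should be fixed, but it gives no reason to change the sample size.

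**What to change.** Keep N=120.

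1. **Statistical Analysis Plan and the Statistical Methodology row.** Name the treatment comparison for each measure as an ANCOVA of the post-treatment value, with group as factor and the pre-treatment value of the same measure as covariate. Compare pairs on adjusted means with Bonferroni correction, in place of Tukey. Keep the Levene check and add a check of equal slopes. Where normality is not met, apply Kruskal-Wallis and Bonferroni-corrected Mann-Whitney tests to the change from pre to post. Keep the repeated-measures ANOVA and Friedman sentences for the time analysis.

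2. **Sample Size.** Keep the account of how 120 was derived. Add that it is for the between-group effect on the pre/post average, and give the correlation used (about 0.5 reproduces it). Then add: *Assuming equal allocation, f=0.25 on the post-treatment value and alpha 0.05 for one measure, 120 participants give the ANCOVA power 0.72, 0.80 and 0.93 at pre-post correlations of 0.3, 0.5 and 0.7.* State that the agreement with 0.80 at correlation 0.5 is a coincidence, because 1−rho² and (1+rho)/2 both equal 0.75 there, and does not confirm the sizing. If 0.25 was meant on the pre/post average, say so and give the implied post-treatment f of 0.50.

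**Cost.** Text edits only, with no extra participants or measurements. The stated power becomes conditional and falls below 0.80 if the correlation is under about 0.49. Bonferroni is slightly more conservative than Tukey. The rank fallback on change has less power than the ANCOVA, and at correlation 0.3 less than Kruskal-Wallis on post values (0.50 against 0.66, simulated with normal data).

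### Do the differing eligibility lists in the Study Summary and the body call for a change to the plan?

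*Combined protocol and SAP*

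**What the plan says.** Eligibility is stated twice.

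The Subjects row of the Study Summary puts everything under inclusion criteria. It begins "To determine if a participant is healthy a score of 5 or less on the neck disability index will be used". It then asks for "no history of cervical trauma, rheumatic diseases, whiplash syndrome", no earlier surgery in the neck, face or shoulder region, "no history of cancer, no history of systemic diseases, age of 18 or above", and the ability to follow instructions.

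The body has two headed lists. Inclusion Criteria has three entries: the same index threshold, the ability to follow instructions, and "Above 18 years old". Exclusion Criteria has six: cervical trauma, "History of cervical inter-vertebral disc pathology", rheumatic diseases, whiplash syndrome, earlier surgery in the same regions, and "History of systemic diseases".

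The Randomization and Procedures section says that those who had consented and met the inclusion criteria received a number tied to a group. It does not say which of the two lists is meant.

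**The concern.** Read literally, the two lists admit different people. A volunteer with a past disc problem, few current symptoms and a low index score passes the Summary and fails the body. A volunteer with a cancer history fails the Summary, and may pass the body if cancer is not read as a systemic disease. The wording of the age limit also matters for someone aged exactly 18. The plan says "Participants will be recruited from university campus by directly asking students from classes if they can volunteer", so such volunteers are conceivable, although the documents give no age distribution.

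Two things would be at stake. The first is screening: in the PNF pattern arm the therapist will "apply resistance throughout the ROM", the stretching arm combines stretch with isometric contraction, and neck strength is measured with no restriction by arm. The second is the description of the healthy population to which the results apply.

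**Working it through.** **Step 1: the lists side by side.**

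| Item | Study Summary | Body |
|---|---|---|
| Neck disability index, at most 5 | yes | yes |
| Follows instructions | yes | yes |
| Surgery (neck, face, shoulders) | yes | yes |
| Systemic diseases | yes | yes |
| Cervical trauma | yes, as history | yes, no mention of history |
| Rheumatic diseases | yes, as history | yes, no mention of history |
| Whiplash | yes, as history | yes, no mention of history |
| Age | at least 18 | over 18 |
| Cancer | yes | not named |
| Disc pathology | not named | yes |

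Each list has 9 items and 8 appear in both, so there are 9 + 9 - 8 = 10 distinct items. Four match apart from trivial phrasing, four differ in wording, and two appear in one list only (4 + 4 + 2 = 10). If cancer falls under systemic diseases, there are 9 distinct items and only the disc item is unmatched.

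**Step 2: what each difference amounts to.**

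- *Disc pathology.* A summary table may leave out an item that the full list states. The headed list excludes this volunteer, who would enter only if a screener worked from the Summary alone.
- *Cancer.* This is the harder item, because abbreviation cannot explain why the longer list lacks something the summary has. The Summary also names cancer separately from systemic diseases, which weighs against treating it as already covered in the body.
- *Age.* The two phrases differ only for a person aged exactly 18, and are probably loose wording for adults.
- *History of.* In a list meant to select healthy volunteers, trauma and whiplash are naturally read as past events, and the Summary supports that reading.

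**Step 3: do the lists conflict?** Neither says that a person with a disc or cancer history may be enrolled. A person who satisfies all 10 items satisfies both lists, and anyone over 18 is also at least 18. The lists are incomplete relative to each other but compatible.

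**Step 4: does any calculation depend on the difference?** The only computed figure is the total of 120. For a between-groups repeated-measures ANOVA, λ = N × f² × m / (1 + (m - 1)ρ), with N = 120, f = 0.25 and m = 2 from the Sample Size paragraph. The documents do not give ρ. Assuming 0.5, λ = 120 × 0.0625 × 2 / 1.5 = 10. With 2 and 117 degrees of freedom at alpha 0.05, power is 0.805; a total of 117 gives 0.794. The stated 120 is therefore reproduced under that assumption. Across ρ from 0 to 0.9 the required total runs from 81 to 150. None of these inputs is an eligibility item.

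**Step 5: can it bias the comparison?** By the Randomization and Procedures section, criteria are met before a number is assigned, and a person external to the study does the randomization. Whichever list was used, it acted before allocation and equally on all three groups.

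**The case for a change.** The strongest case for acting is that each list names something the other lacks, so neither can be taken as complete. The procedures section does not settle the matter: its reference to inclusion criteria could mean the Summary, where every item carries that label, or the body, where only three do and the disc item sits among the exclusions. The word healthy does not help, because the Summary ties it to an index score that a person with a disc history could meet. The interventions work the neck, so neck-related screening is not a trivial matter.

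Much of this stands. The texts differ, the document does not say which governs, and the cancer item is not explained by abbreviation. What does not stand is the step from there to a consequence. The documents give no safety rationale for the individual criteria and no count of volunteers affected, so an effect on safety is possible but not shown. The age point cannot be treated both as loose wording for adults and as a material difference.

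**Conclusion.** This is a clerical mismatch and no change to the plan follows. It comes to two items named in one list only, or one if cancer is read as a systemic disease, together with four differences of wording that probably carry no difference in intent. The number of volunteers affected cannot be worked out from the documents. The randomised comparison, the sample size and the planned tests are the same under either list, and the conclusions would be sound under either.

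This rests on two assumptions: that one list was applied consistently to all volunteers, and that screening came before allocation, as the procedures section describes. The two statements of eligibility should be reconciled as a matter of editing, and a report should say which criteria were used. The content of the list is for the sponsor to decide.

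### A Kolmogorov-Smirnov test chooses between mean-based and rank-based analyses that do not answer the same question, and the choice brings no type I error benefit

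*Combined protocol and SAP*

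**What the plan says.** The Statistical Analysis Plan and the Statistical Methodology row of the Study Summary carry the same text. Normality is examined first: "The variables investigated using Kolmogorov Smirnov test to determine whether or not they are normally distributed". Two sets of tests follow.

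- Mean-based: "Since the variables are normally distributed, ANOVA will be used to compare the means of the groups", with Tukey post hoc. For change over time, "the effect of time change in measurements will be investigated by Repeated Measures ANOVA test".
- Rank-based: "Since the variables are not normally distributed Kruskal-Wallis test will be used to compare the groups", with Bonferroni-corrected Mann-Whitney tests. For change over time, "Since the variables are not normally distributed Friedman test will be used", with Bonferroni-corrected Wilcoxon tests.

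The significance level is fixed: "A 5% type-I error level was used to infer a statistical significance". The text does not say which version of K-S is used (plain or Lilliefors-corrected), whether it is run pooled or by arm, or at which measurement. It mentions no residuals, no default test, and no rule that keeps related measures on one test.

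The Assessment Methods section defines six proprioception, six active range-of-motion and six strength measures, with right and left separate: 3 x 6 = 18. The Sample Size paragraph plans a repeated-measures ANOVA with between factors at 80% power and a 5% alpha. Its remaining inputs and its result are given as "effect size of 0.25 with number of measurements being 2, which total to 120 participants".

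**The concern.** Read literally, the text asserts two incompatible facts about the same data and so names no single method. Read charitably, it is a conditional rule in which trial data select the test. The selection then needs a reason, and the usual one is protection of the 5% level. If ANOVA already holds that level at this sample size, the gate adds only uncertainty about which analysis will be reported.

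That uncertainty matters because the branches are not two routes to one answer. The trial asks whether the arms change differently between the two measurements. A repeated-measures ANOVA can carry an arm-by-time term. Kruskal-Wallis compares arms on one set of values, and Friedman compares times without regard to arm. A measure that fails K-S could therefore lose the comparison the trial was set up to make, and two sides of the same movement could be reported on different footings.

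**Working it through.** **1. The plan's own figure.** Inputs from Sample Size: f = 0.25, alpha 0.05, m = 2 measurements, power 0.80. The Study Summary gives k = 3 arms. The correlation rho between measurements is not stated; 0.5 is assumed. For the between-factors test, lambda = f^2 x N x m / (1 + (m - 1) x rho), with k - 1 and N - k degrees of freedom. At N = 120, lambda = 0.0625 x 120 x 2 / 1.5 = 10.0 and power is 0.805. At N = 117, the next smaller multiple of three, lambda = 9.75 and power is 0.794. So 120 reproduces. The other forms tried do not give it: one-way ANOVA 159, within factor 36 and interaction 42 (the last two at rho = 0.5). The total belongs to repeated-measures ANOVA, and nothing was computed for the rank branch.

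**2. Does the gate protect the 5% level?** Simulation: three arms of 40 (allocation ratio not stated, equal assumed), identical distributions across arms, 20,000 runs per scenario, Monte Carlo standard error sqrt(0.05 x 0.95 / 20,000) = 0.0015. Assumed shapes: normal, gamma with skewness 0.7 and 1, t with 5 df, half-normal, lognormal with sigma 0.5 and 1.

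| Rule | Type I error |
|---|---|
| Always ANOVA | 4.1-5.1% (lowest for lognormal, sigma 1) |
| Always Kruskal-Wallis | 4.6-5.1% |
| K-S gate, all versions | 4.6-5.4% |

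A smaller separate check gave 5.1-5.6% for ANOVA and 5.1-6.0% for the gate. A fixed model adjusted for the first measurement gave 5.1% (normal, gamma, half-normal) and 4.3% (lognormal, sigma 1).

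**3. Can right and left part company?** Same simulation, both sides with the same distribution and correlation 0.5 or 0.8. Percentage of pairs in which the two sides are sent to different branches:

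| Shape | Lilliefors, pooled | Lilliefors, any arm | Plain K-S, pooled |
|---|---|---|---|
| Normal | 9-10 | 23-25 | 0 |
| Skewness 0.7 | 41-49 | 44-49 | 4-5 |
| Skewness 1 | 28-33 | 37-41 | 17-19 |
| t, 5 df | 38-46 | 43-48 | 5-6 |
| Half-normal | 6-7 | 23-25 | 32-36 |
| Lognormal, sigma 0.5 | 4-5 | 11-12 | 39-47 |
| Lognormal, sigma 1 | 0 | 0 | about 0 |

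The plan fixes none of the columns, and the rows are assumptions.

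**4. Friedman with two measurements.** Ranking two values per participant leaves only the sign of the difference, so the Friedman statistic is (2S - n)^2 / n, where S is the number of increases. Take n = 40 (one arm) and normal differences. A paired t-test has 80% power at a standardised mean difference of 0.454. Then P(increase) = Phi(0.454) = 0.675. The 5% chi-square cutoff of 3.84 needs S >= 27 or S <= 13, and the binomial probability is 0.575. Power falls from 80% to about 57%. The large-sample efficiency is 2/pi = 0.64.

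**5. Power of the between-arm test.** Three arms of 40, f = 0.25, 1,500 runs, pooled K-S, assumed shapes. Lognormal with sigma 0.5: ANOVA 0.69, gated 0.73 (Lilliefors) or 0.72 (plain), a gain of 3-4 points. Normal and mixed-sex strength: a loss of under 1 point. Mean of three absolute errors: a loss of 3-4 points with Lilliefors and under 1 point with plain K-S.

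**The case against.** The strongest reply is that the harm to the between-arm test is small. Both branches are valid at close to 5%, their post hoc tests are named in advance, and the rule is mechanical. All of that stands. A reader might infer that the gate inflates type I error or lets the analyst pick the favourable p-value; the simulations do not show the first, and the text does not support the second. A reader might also infer a general loss of power. Step 5 shows that the effect can go either way, and for skewed measures ranks may do better. That argues for choosing a scale or a rank method beforehand, not for a gate.

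The text speaks of the variables collectively. Testing each one separately, and on raw values, is the natural reading but an inference. If K-S is run within arm, it does examine the residual assumption of one-way ANOVA, so the complaint about raw values applies to pooled testing of post-treatment data. Right and left can be split; the documents do not support saying that they will be.

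On the arm-by-time point, Kruskal-Wallis on change scores would supply the comparison, but the plan does not mention change scores. Nor does it name the arm-by-time term in the mean-based branch: it describes repeated-measures ANOVA only for the effect of time. The difference is that this model can carry the term and Friedman cannot. Finally, the listed Wilcoxon test would lose far less power than Friedman. With two measurements there is only one pair, so the two tests would address the same contrast, and the plan does not say which decides. The loss in step 4 applies where Friedman decides.

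**Conclusion.** The concern holds in a limited form and should be corrected. The two statements about normality cannot both be true, and the implied gate is not specified well enough for two analysts to reach the same test. It brings no type I error benefit at about 40 per arm, under the assumed shapes and equal distributions across arms. Discordance between sides lies anywhere from about 0% to 49%; that width reflects what the plan leaves open and is not an estimate for this trial.

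The weight of the point is in the mismatch of branches. The rank branch as written has no arm-by-time comparison, its Friedman test is a sign test with about 57% power against 80% (normal differences, n = 40), and the sample size was not computed for it. The effect of the gate on between-arm power is at most a few points in either direction and does not carry the argument.

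**What to change.** In both the Study Summary and the Statistical Analysis Plan, delete the K-S step and both statements about normality. Name one model for all 18 measures: a linear model of the second measurement on arm, adjusted for the first measurement, with Tukey-adjusted pairwise comparisons of arms. If the repeated-measures ANOVA is kept instead, name its arm-by-time term as the test for every measure; one of the two must be written down before data are seen, not left as a choice.

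Check residuals by plot. Define the proprioception error score, which the plan does not do, and fix one scale for it in advance, for example the square root of absolute error. Report Kruskal-Wallis tests on change scores for every measure as a sensitivity analysis that cannot replace the main result. State in Sample Size which term the 120 refers to, since the form that reproduces it is the between-arm test over both measurements.

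The cost is wording: dropping the gate changes neither the number of participants nor data collection. The downside is that skewed measures will rest on the pre-set scale, and ranks might have had slightly more power for some of them.
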